### **9.2 Determination of Sample Size**

This is a Phase 1b/2 dose escalation and dose expansion study. During dose escalation (Phase 1b), successive groups of at least 3 patients will be treated at each dose level until the MTD and/or RP2D is determined. Additional patients may be added to each dose level based on the scheme and rules outlined in Section 5.2.3.4 or Sponsor determination of the need for additional data to further evaluate the benefit/risk profile. It is estimated that approximately 30 patients will be enrolled in the dose escalation.

A Bayesian design will be used CCI [REDACTED].

For HNSCC and CRC cohorts, an initial 12 patients will be enrolled into stage 1 of Cohorts A and B, respectively, and the enrollment will continue to a maximum of 24 patients or until the criteria of  $\text{Pr}(\text{ORR} > 0.25 | \text{Data}) > 30\%$  is met. Patient enrollment to Cohorts A1 and B1 will be gated by the Bayesian criteria. After the initial 5 patients' first tumor assessment, subsequent patients will be randomized to the second stage of Cohort A versus Cohort A1, and the second stage of Cohort B versus Cohort B1 using adaptive randomization.

With adaptive randomization, patients will be adaptively assigned proportional to weighted clinical utility function based on available response data. Higher scores are assigned to better responses: [CR  $\geq$  6m = 6], [CR = 5], [PR  $\geq$  6m = 4], [PR = 3], [stable disease (SD)  $\geq$  6m = 2], [SD = 1], [progressive disease = 0], thus a new patient will have higher chance to be assigned to the cohort with better responses. A minimum of 0.1 allocation probability will be retained for each cohort. A maximum of 50 patients each will be enrolled into Cohort A and Cohort B, and a maximum of 26 patients each will be enrolled into Cohort A1 and Cohort B1.

Prior for ORR is set to be Beta(0.25,0.75) corresponding to a prior belief of ORR = 0.25 with 1 effective sample. The following Bayesian decision rules will be applied to Cohort A, Cohort A1, Cohort B, and Cohort B1, respectively, to guide the Go/No-Go decision:

- Select an arm as superior if

- $\text{Pr}(\text{ORR} > 0.25 | \text{Data}) > 80\%$  and  $\text{Pr}(\text{ORR} > 0.10 | \text{Data}) > 90\%$
- Suspend accrual to an arm if  $\text{Pr}(\text{ORR} \leq 0.10 | \text{Data}) > 85\%$
- Achieve maximum sample size

CCI

With adaptive randomization, patients will be adaptively assigned proportional to weighted clinical utility function based on available response data. Higher scores are assigned to better responses: [CR  $\geq$  6m = 6], [CR = 5], [PR  $\geq$  6m = 4], [PR = 3], [SD  $\geq$  6m = 2], [SD = 1], [progressive disease = 0], thus a new patient will have higher chance to be assigned to the cohort with better responses. A minimum of 0.1 allocation probability will be retained for each cohort.

CCI

Prior for ORR is set to be Beta(0.25, 0.75) corresponding to a prior belief of ORR = 0.25 with 1 effective sample. The following Bayesian decision rules will be applied to Cohort C, Cohort C1, Cohort D, Cohort D1, Cohort E, and Cohort E1, respectively, to guide the Go/No-Go decision:

- Select an arm as superior if
  - $\text{Pr}(\text{ORR} > 0.25 | \text{Data}) > 80\%$  and  $\text{Pr}(\text{ORR} > 0.10 | \text{Data}) > 90\%$
- Suspend accrual to an arm if  $\text{Pr}(\text{ORR} \leq 0.10 | \text{Data}) > 85\%$
- Achieve maximum sample size

### 9.3 Safety Stopping Rules

A Bayesian sequential monitoring design ([Thall, 1995](#)) will be employed to monitor safety of all patients enrolled in the study after 6 patients have been treated. See Section [5.5.4](#) for details.

### 9.4 Interim Analyses

No interim analyses are planned for this study.

### 9.5 Analysis Sets

Safety Population: All patients who receive at least 1 dose (or partial dose) of NKTR-255

Cetuximab-only Population: All patients who receive at least 1 dose (or partial dose) of cetuximab but without any dose of NKTR-255

DLT Population: All patients who receive at least 1 dose of the combination treatment of NKTR-255 and cetuximab and who complete the DLT observation period or discontinue from the study treatment due to a DLT will be included, where DLT window is 21 days since the first dose of NKTR-255.

Pharmacokinetic Population: All patients in the Safety Population who have evaluable analyte concentration-time profiles that allow for the computation of meaningful PK parameter values.

CCI  
[REDACTED]

CCI  
[REDACTED]

Response-evaluable Population: The Response-evaluable Population is defined as patients who have measurable disease (per RECIST 1.1) at baseline, receive at least 1 dose (or partial dose) of study drug, and have at least 1 post-baseline assessment of tumor response.

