### **5.2.3.4 Replacement of Patients**

In the dose escalation portion, patients who do not complete the DLT observation period for reasons other than a DLT may be replaced to provide a sufficient number of patients for adequate evaluation of each dose escalation level.

Patients will not be replaced during the dose expansion portion of the study.

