### 5.3.1.5 NKTR-255 Dose Delay and Adjustment Criteria

NKTR-255 dose adjustments may only be performed with approval of the Sponsor’s Medical Monitor. Dose adjustments of NKTR-255 within a single patient are not permitted within the DLT window. Outside of the DLT window in the dose escalation phase and during dose expansion, dose levels of NKTR-255 may be reduced depending on the severity, duration, and frequency of toxicities observed at the previous dose level tested (the dose level may be de-escalated in order to characterize RP2D for a specific cohort).

NKTR-255 doses may be delayed or reduced per the recommendation of the Investigator and approval of the Sponsor’s Medical Monitor, based on observed drug-related toxicities for the following reasons:

- Grade 1 or 2 toxicity: No requirement for dose delay or dose reduction. If the toxicity persists at Grade 2 following completion of the cycle, a dose delay or dose reduction may be implemented in consultation with the Medical Monitor.
- Grade 3 toxicity: NKTR-255 may be withheld if toxicity cannot be managed by adequate medical intervention. NKTR-255 dosing may resume at one dose level lower when toxicity resolves to Grade 1 or returns to baseline, except for instances where the potential recurrence of the event poses an undue risk for the patient.
- Grade 4 non-hematological toxicity that is not considered by the Investigator to be attributable to another identifiable cause: dosing should be permanently discontinued.
- For specific severe or medically important toxicities that require permanent treatment discontinuation, refer to Section [5.7](#).

Tumor assessments for all patients should continue as per protocol even if dosing is delayed. Grading of AEs is described in Section 7.3.

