##### **5.5.1 Dose-Limiting Toxicities Related to NKTR-255 and Cetuximab**

Examples of AEs related to NKTR-255 or NKTR-255 combined with cetuximab that are defined as a DLT include the following:

1. Any Grade  $\geq 3$  non-hematological AE except those listed in Section 5.5.2
2. Any Grade 4 hematological AE, including neutropenia, leukopenia, thrombocytopenia, and anemia, except those listed in Section 5.5.2
3. Any Grade 3 thrombocytopenia with bleeding
4. Any case meeting the Hy's law criteria (<https://www.fda.gov/downloads/Guidances/UCM174090.pdf>)
5. Any Grade  $\geq 3$  ( $> 5x$  ULN) AST/ALT elevation

6. Any Grade  $\geq 3$  ( $> 3x$  ULN) total bilirubin elevation
7. Any Grade 4 nausea or vomiting
8. Any Grade 4 amylase or lipase elevation
9. Death not clearly due to underlying disease or extraneous causes or disease progression

Laboratory findings indicating a DLT should be reconfirmed by the local laboratory within 24 hours.

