## 5.7 Permanent Treatment Discontinuation Criteria

Patients meeting any of the following criteria will be required to permanently discontinue all assigned study drug(s). However, with Medical Monitor approval, NKTR-255 treatment may continue if the toxicities listed below are considered related to cetuximab only.

- Progressive disease per RECIST 1.1 (see details regarding continuing treatment beyond initial assessment of progression, Section 5.2.5)
- Clinical deterioration, as assessed by the Investigator
- Grade 3 or 4 CRS (Lee, 2014)
- Grade 3 or 4 IRR
- Grade 4 rash

- Grade 3 laboratory abnormalities require treatment discontinuation for the following:
  - Grade 3 thrombocytopenia  $> 7$  days associated with clinically significant bleeding requires discontinuation.
- Any Grade 4 AE or laboratory abnormality, except for the following events, which do not require discontinuation:
  - Grade 4 neutropenia  $\leq 7$  days
  - Grade 4 lymphopenia or leukopenia
  - Isolated Grade 4 electrolyte imbalances/abnormalities that are not associated with clinical sequelae and are corrected with supplementation/appropriate management within 72 hours of their onset
- Any AE, laboratory abnormality, or intercurrent illness, which, in the judgment of the Investigator, presents a substantial clinical risk to the patient with continued treatment.
- Any dosing delay lasting  $> 2$  weeks after completion of the prior cycle, with the following exceptions (see Section [5.3.1.5](#) for dose delay and adjustment criteria):
  - Patient has not started any new therapy.
  - Dosing delays to allow for prolonged steroid tapers to manage drug-related AEs are allowed. Tumor assessments should continue as per protocol even if dosing is delayed.
  - The Investigator and the Medical Monitor may agree to a longer dose delay following a clinically significant AE if the patient is deriving clinical benefit from the regimen as defined by CR, PR, or stable disease, up to 6 weeks from last dose of either of the 2 investigational agents, per RECIST 1.1. Any delay beyond 6 weeks must be discussed with the Medical Monitor and approval documented.

Tumor assessments should continue as per protocol even if dosing is delayed, and patients must otherwise meet the criteria for continued treatment at the time re-initiation of study therapy is considered (see Section [5.11](#)).

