## 7.5 AE Reporting and Follow-up

All AEs, except for SAEs (Section 7.7) and AEs attributed to protocol-mandated procedures (Section 7.2), will be reported from the time of first study drug(s) administration until 60 days after the last dose of study treatment, unless the patient withdraws consent to treat, initiates new anti-cancer therapy, is lost to follow up, or death occurs. All ongoing AEs will be followed until resolution, the patient is lost to follow-up, patient death, or until 60 days after the last dose of study treatment. In case the AE has not completely resolved up to 60 days after the last dose of study treatment or until a new antineoplastic regimen has been initiated, the final outcome of these ongoing AEs will be captured as "Not Recovered/Not Resolved" or "Recovering/Resolving", whichever is applicable.

For specific instructions on identifying and reporting SAEs, see Sections 7.6 and 7.7.

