### 6.3 Analysis Populations

**Enrolled Population:** All patients who receive at least 1 dose (or partial dose) of cetuximab or NKTR-255.

**Safety Population:** All patients who receive at least 1 dose (or partial dose) of NKTR-255.

**Cetuximab-only Population:** All patients who receive at least 1 dose (or partial dose) of cetuximab but without any dose of NKTR-255.

**DLT Population:** All patients who receive at least 1 dose of the combination treatment of NKTR-255 and cetuximab and who complete the DLT observation period or discontinue from

the study treatment due to a DLT will be included, where DLT window is 21 days since the first dose of NKTR-255.

**Response-evaluable Population:** The Response-evaluable Population is defined as patients who have measurable disease (per RECIST 1.1) at baseline, receive at least 1 dose (or partial dose) of NKTR-255, and have at least 1 post-baseline assessment of tumor response.

**Pharmacokinetic Population:** All patients in the Safety Population who receive at least 1 dose of treatment and have at least one evaluable PK concentration.

CCI

CCI

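### As worded, the DLT Population can omit a patient with an observed in-window DLT who leaves before Day 21 for an unrelated reason

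*Protocol*

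**What the plan says.** Protocol 9.5 places in the DLT Population those who received at least one dose of the combination "who complete the DLT observation period or discontinue from the study treatment due to a DLT will be included". SAP 6.3 repeats the rule ("and who complete the DLT observation period or discontinue from" study treatment due to a DLT) and adds no other route. The window is 21 days from the first NKTR-255 dose.

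The set is used for a primary endpoint. SAP 4.1 names DLT incidence as a Phase 1b primary endpoint. Protocol 9.6.1 evaluates its rate by dose level in the DLT Population, and SAP 7.6.1 summarises DLTs in the same set.

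These passages determine who can fall outside both routes:
- Protocol 5.5.1 item 2 makes this a DLT: "Any Grade 4 hematological AE, including neutropenia, leukopenia, thrombocytopenia, and anemia, except those listed in Section 5.5.2". Section 5.5.2 exempts certain lymphopenia but not leukopenia.
- Protocol 5.7 requires discontinuation for "Any Grade 4 AE or laboratory abnormality, except for the following events, which do not require discontinuation". The listed exceptions include "Grade 4 lymphopenia or leukopenia".
- For Grade 3 toxicity, Protocol 5.3.1.5 says "NKTR-255 may be withheld if toxicity cannot be managed by adequate medical intervention".
- Protocol 5.2.3.4 says "patients who do not complete the DLT observation period for reasons other than a DLT may be replaced".
- Protocol 7.5 collects adverse events to 60 days after the last dose "unless the patient withdraws consent to treat, initiates new anti-cancer therapy, is lost to follow up, or death occurs".

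**The concern.** In a dose-escalation study, a patient with a DLT in the window is evaluable from the moment of the event. What happens afterwards does not change the outcome. Here membership depends on how the patient leaves, not on whether the event occurred. A patient with a DLT that does not lead to discontinuation, who then withdraws consent or is lost to follow-up on, say, Day 12, has neither completed the window nor stopped treatment due to a DLT. Followed literally, the rule discards an event that was seen and recorded, and the replacement rule as worded allows another patient in that patient's place.

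At stake is the accuracy of a primary-endpoint table built on very small groups. Levels have at least 3 patients, and at least 6 are needed to define the RP2D.

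**Working it through.** The plan gives no figure of its own on this point, so there is none to reproduce. The check has a reading part and an arithmetic part.

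**Is there another route?** Protocol 5.2.3.4, 5.4 to 5.5.4, 5.7, 9.3, 9.5 and 9.6.1 and SAP 6.3 and 7.6.1 contain no third route into the set. The replacement rule does not supply one, because it also turns on the reason for not completing the window.

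**Can the case arise?** Take each patient with an in-window DLT:
1. Observed to Day 21: included by the first route, whether or not still on treatment.
2. Stops treatment because of the DLT: included by the second route. Section 5.7 makes this the outcome for many severe events.
3. DLT does not lead to discontinuation, and the patient leaves observation before Day 21 for an unrelated reason: neither route applies. Grade 4 leukopenia (5.5.1 item 2 set against the 5.7 exceptions) shows that the first condition can be met. So does a Grade 3 DLT managed under 5.3.1.5. The circumstances named in Protocol 7.5 show how observation can end. Where the exit is to new therapy the case is narrower, because Protocol 5.2.6 continues follow-up of clinically significant events.

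**Effect of one omitted event on an observed rate** (event counts assumed for illustration; Clopper-Pearson 95% intervals, the method in SAP 6.1):
- 2/6 = 33.3% (4.3 to 77.7%) if counted.
- (2−1)/(6−1) = 1/5 = 20.0% (0.5 to 71.6%) if dropped.
- 1/6 = 16.7% (0.4 to 64.1%) if dropped and replaced by a patient without a DLT.
- Likewise 1/6 = 16.7% becomes 0/5 = 0% (0 to 52.2%), or 0/6 = 0% (0 to 45.9%) after replacement.

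**Expected rate under each rule.** Let p be the true DLT rate, qd the share of DLT patients who leave through the gap, and qn the share of DLT-free patients who leave early.
- Current rule: p(1−qd) / [p(1−qd) + (1−p)(1−qn)].
- Rule that keeps every in-window DLT: p / [p + (1−p)(1−qn)].

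The documents give no exit rates. Assume p = 0.33 and let qd and qn each range from 2% to 10%:
- qd 10%, qn 2%: current 0.297/(0.297 + 0.6566) = 31.1%, error −1.9 points.
- qd 2%, qn 10%: current 0.3234/(0.3234 + 0.603) = 34.9%, error +1.9 points.
- qd 10%, qn 10%: current 0.297/(0.297 + 0.603) = 33.0%, error 0.
- Alternative rule, qn 2%: 0.33/(0.33 + 0.6566) = 33.4%, error +0.4.
- Alternative rule, qn 10%: 0.33/(0.33 + 0.603) = 35.4%, error +2.4.

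Over this range the current rule errs by −1.9 to +1.9 points and the alternative by +0.4 to +2.4.

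**The case against.** The strongest case against the point is that the gap is narrow and has no shown effect on any decision.

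- The second route speaks of stopping due to a DLT and does not require a particular reason code on a form. A patient who withdraws because of the DLT fits the words. This stands, so the gap concerns only exits unrelated to the DLT.
- The first route is completing observation, not treatment. NKTR-255 is given every 21 days, so withholding it concerns a later dose and removes nobody from observation. Patients off treatment are still followed for safety. This also stands: several things must coincide, in patients who entered with ECOG 0 or 1 and a life expectancy above 12 weeks.
- The event remains visible. SAP 7.6.1 lists all DLTs by patient, and the event stays in the treatment-emergent tables for the Safety Population. A reader could recompute the rate.
- The SAP describes Phase 1b enrolment in the past tense and says no Phase 2 patients were enrolled, so rewording the replacement rule may change nothing in practice.

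None of this supplies the missing route. It limits how often the gap matters and how far it reaches.

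A reader might infer that escalation or suspension decisions are compromised. The documents do not support that. Protocol 9.3 applies the suspension rule to all enrolled patients. Neither Protocol 5.8 nor Appendix 1 names the analysis set that feeds the BLRM. If it were the DLT Population, one DLT in 3 patients at 1.5 µg/kg would give a posterior probability of 0.418 that the DLT rate is at least 33%, against 0.089 for 0/2 and 0.050 for 0/3, on either side of the 25% overdose limit. That rests on an input set that the documents do not state, and model output is guidance to be combined with clinical assessment.

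**Conclusion.** The point holds as a minor defect of wording. Followed exactly, the definition can drop an observed primary-endpoint event from the DLT rate at a dose level. Where that happens in a level of six, the reported rate moves from 33.3% to 20.0% or 16.7%. The consequence is confined to the DLT incidence table.

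Two stronger readings should be resisted. First, a reader might put a probability on the omission. That needs a DLT rate and an exit rate, and the documents give neither, so any such figure is only the assumption restated. Second, a reader might infer that the current rule systematically understates toxicity. It does so only if early exit is more common after a DLT than without one. With equal exit rates it is unbiased, and over the assumed 2% to 10% range its error is centred on zero.

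Confidence is high that the route is absent from the text. Practical impact cannot be judged without knowing whether any such patient exists.

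**What to change.** In SAP 6.3, recorded as a change in SAP 12.0, and in Protocol 9.5, define the DLT Population as patients who receive the combination and either have a DLT within the 21-day window, whatever the reason for later exit, or complete the window without a DLT. If the protocol is amended, reconcile the wording of 5.2.3.4 so that a patient with an in-window DLT is not treated as non-evaluable.

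The cost is one sentence in each document and no new data. No dose or clinical rule changes, and if no such patient exists no result changes. The downside is that DLT-free early leavers stay excluded while every DLT patient is kept, so the rate leans upward: a true 33% would read 33.4% to 35.4% if 2% to 10% of DLT-free patients leave early. The reason to accept this is that an observed primary-endpoint event is never discarded and any error is on the cautious side. It is not that the estimate is always closer to the truth.

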### **5.2.3.1 Criteria for Discontinuation from Treatment**

Study treatment may be discontinued for any of the following reasons:

- Any clinical AE, laboratory abnormality, or intercurrent illness that would, in the judgment of the Investigator, affect assessments of clinical status to a significant degree
- Toxicity that, despite maximum medical management, in the judgment of the Investigator, compromises the ability to continue study-specific procedures or is considered to not be in the patient's best interest
- Disease progression (based on Investigator assessment of baseline and post-baseline scans as per RECIST 1.1). In some circumstances patients may be treated beyond disease progression. Details are provided in Section [5.2.5](#).
- Patient request to discontinue treatment for any reason
- Patient noncompliance
- Initiation of systemic antineoplastic therapy other than treatments per protocol in the absence of progression
- Discontinuation of the study treatment at the request of Nektar, a regulatory agency or an institutional review board (IRB) or independent ethics committee (IEC)
- Pregnancy during treatment
- Death
- Investigator's decision, in consultation with the Medical Monitor

If a patient discontinues NKTR-255, the patient may continue on cetuximab alone, at the discretion of the Investigator, until disease progression or initiation of systemic anti-tumor therapy (whichever is earlier).

If a patient discontinues study drug(s), every attempt should be made to continue tumor assessment at every 9 weeks until disease progression or initiation of systemic anti-tumor therapy. The patient will be asked to attend the 60-day post-treatment follow-up assessment visit when discontinuing from the study treatment.

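### The DLT Population has no entry route for an in-window DLT as such, so a patient whose DLT does not stop treatment and who leaves before Day 21 for another recorded reason drops out of the primary DLT rate

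*Protocol*

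**What the plan says.** Protocol 9.5 requires at least one dose of the combination and then limits the set to patients "who complete the DLT observation period or discontinue from the study treatment due to a DLT will be included". SAP 6.3 carries the same condition ("who complete the DLT observation period or discontinue from" study treatment because of a DLT), and SAP 12.0 lists no change to it. The window is 21 days from the first NKTR-255 dose.

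Protocol 9.6.1 and SAP 7.6.1 compute DLT incidence in this set, and SAP 4.1 makes it a Phase 1b primary endpoint. SAP 7.6.1 also lists all DLTs by patient.

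On what counts as a DLT, Protocol 5.5.1 includes "Any Grade 4 hematological AE, including neutropenia, leukopenia, thrombocytopenia, and anemia, except those listed in Section 5.5.2". On stopping, 5.3.1.5 says: "Grade 3 toxicity: NKTR-255 may be withheld if toxicity cannot be managed by adequate medical intervention". Section 5.7 requires permanent discontinuation for "Any Grade 4 AE or laboratory abnormality, except for the following events, which do not require discontinuation", and the exceptions include "Grade 4 lymphopenia or leukopenia" and Grade 4 neutropenia lasting no more than 7 days. Section 5.2.3.1 gives reasons for leaving treatment that are separate from toxicity, among them "Patient request to discontinue treatment for any reason". Section 5.2.3.4 allows replacement when the window is not completed for a reason other than a DLT.

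**The concern.** The population rule assumes that a patient with a DLT either reaches Day 21 or stops because of the DLT. The protocol's own DLT and discontinuation sections leave a third course: a DLT that does not require stopping, followed by early departure for a different recorded reason. Under the written rule that patient is treated like someone who left early without a DLT, and the replacement rule, which looks at the reason for leaving, permits a substitute.

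A known DLT would then be absent from the primary rate at its dose level. Groups are small enough for one patient to change what the table shows.

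**Working it through.** **1. Is a DLT always a reason to stop?** For events in the window that are drug-related:

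| Event | DLT? | Stop required? |
|---|---|---|
| Grade 4 leukopenia | Yes: 5.5.1 item 2; the only hematological exemption in 5.5.2 is lymphopenia | No: 5.7 exception |
| Grade 4 neutropenia, 7 days or less | Yes: 5.5.1 item 2 | No: 5.7 exception |
| Grade 3 rash not improved within 7 days | Yes: 5.5.1 item 1 read with 5.5.2 item 6 | Not in visible 5.7, which lists Grade 4 rash; 5.3.1.5 makes withholding optional |
| Grade 3 AST/ALT or bilirubin | Yes: 5.5.1 items 5 and 6 | Unsettled: 5.3.1.6 points to combined liver parameters in 5.7 that the visible text does not show |

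**2. Who enters the set?**

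| Course | Completes 21 days | Stops due to DLT | In set |
|---|---|---|---|
| DLT, observed to Day 21 | Yes | Either | Yes |
| DLT, treatment stopped because of it | No | Yes | Yes |
| No DLT, leaves early | No | No | No, as intended |
| DLT not requiring a stop, leaves before Day 21 for another recorded reason | No | No | No: the gap |

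**3. Size at one dose level.** One omitted DLT patient, replaced by a patient without a DLT (exact Clopper-Pearson 95% intervals):

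- 1/4 = 25% (0.6 to 80.6%) becomes 0/3 = 0% (0 to 70.8%).
- 1/7 = 14.3% (0.4 to 57.9%) becomes 0/6 = 0% (0 to 45.9%).

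**4. How likely is one such case?** The documents give no frequency. Let p be the DLT probability, s the share of DLTs not requiring a stop, and r the share of those patients leaving early for another reason. All three are assumed; n = 30 is the planned Phase 1b size. The chance of at least one case is 1 − (1 − p·s·r)^30:

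- p = 0.16, s = 0.5, r = 0.02: 1 − 0.9984^30 = 0.05.
- p = 0.25, s = 0.5, r = 0.05: 1 − 0.99375^30 = 0.17.
- p = 0.33, s = 0.5, r = 0.10: 1 − 0.9835^30 = 0.39.

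Lower doses would have lower p, and s may be below 0.5, so smaller values are possible.

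**5. Direction in the long run.** Let f = 1 − s be the share of DLTs that force a stop, and e1 and e0 the early-leaving rates among other DLT patients and DLT-free patients. Put K = p[f + (1 − f)(1 − e1)].

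- Current rule: K / [K + (1 − p)(1 − e0)].
- Rule counting every in-window DLT: p / [p + (1 − p)(1 − e0)].

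With p = 0.25, f = 0.5 and e1 = e0 = 0.05, the current rule gives 0.24375/(0.24375 + 0.7125) = 25.5% and the amended rule 0.25/(0.25 + 0.7125) = 26.0%. With e1 = 0.20, the current rule gives 0.225/(0.225 + 0.7125) = 24.0%. The current rate is below the amended rate in both cases, but below the true 25% only in the second.

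**6. If the escalation model uses this set.** The model and prior in Protocol Appendix 1, integrated on a grid, give a prior effective sample size of 0.915 to 0.917 at 1.5 to 12 µg/kg. This agrees with the stated 0.9 to 1. The posterior probability that the DLT rate is 33% or more (overdose limit 0.25) is then:

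| Data | Dose assessed | DLT omitted | DLT counted |
|---|---|---|---|
| 0/3 or 1/4 at 1.5 | 1.5 | 0.050 | 0.288 |
| 0/3 or 1/4 at 1.5 | 3 | 0.140 | 0.538 |
| 0/3 at 1.5, then 0/6 or 1/7 at 3 | 4.5 | 0.031 | 0.175 |
| 0/3 at 1.5, then 0/6 or 1/7 at 3 | 6 | 0.069 | 0.290 |

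Doses above 1.5 are illustrative because the dose list is redacted. One omission can reverse the overdose check, but does not always do so.

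**The case against.** The strongest reply is that the gap needs three things together: an in-window DLT that does not lead to stopping, departure before Day 21, and a recorded reason other than the DLT. NKTR-255 is given every 21 days, so optional withholding after Grade 3 mainly concerns Cycle 2. Protocol 5.2.3 and 5.2.6 keep patients who stop treatment under safety follow-up, the SRC reviews safety before each escalation, and replacement is optional. All of this stands and makes the gap narrow. It does not cover withdrawal of consent or loss to follow-up, both of which end AE reporting under 7.2. Nor does the DLT listing put an omitted patient back into the rate.

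A reader might infer more than the documents support:

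- **That staying on treatment after a DLT excludes a patient.** It does not; such a patient normally completes the window and is counted.
- **That a partial first infusion excludes a patient**, because the Safety Population says "All patients who receive at least 1 dose (or partial dose) of NKTR-255" and the DLT Population omits the parenthesis. The SAP's PK Population omits it too, although it is a subset of the Safety Population. A Grade 3 or 4 infusion reaction requires discontinuation under 5.7, so the patient meets the second condition.
- **That the reported rate must fall below the true rate.** Early leavers without a DLT are also excluded, which pushes the other way.
- **That a case is likely.** Setting s to 100% with p = 0.33 and r = 0.10 gives 63%, but 5.7 requires stopping for most Grade 4 events and for Grade 3 or 4 CRS and infusion reactions.
- **That escalation was affected.** No visible text says which set feeds the model, and Protocol 5.8 treats the model as guidance.

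**Conclusion.** The rule is faulty as written, within narrow limits. It can drop a known in-window DLT from the numerator and denominator of a primary endpoint. One case changes the rate at a dose level by 14 to 25 percentage points in the examples and leaves the table and the listing in disagreement. Relative to a rule that counts every in-window DLT, omitting such a patient always lowers the rate; relative to the true rate, the direction depends on who leaves early.

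The conclusion about the wording rests on the visible text alone. The 5%, 17% and 39% chances rest on assumed inputs, and the overdose-check figures hold only if the model uses this population. The SAP (2.0 and 5.0) describes enrolment as past and limited to Phase 1b, so what remains at stake is the reported DLT rate, not past dosing decisions. If no patient followed this course, no table changes.

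**What to change.** In SAP 6.3, define the DLT Population as patients who receive NKTR-255 with cetuximab and meet one of two conditions:

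1. they have a DLT within 21 days of the first NKTR-255 dose, whether that dose was full or partial and whatever the reason for leaving; or
2. they receive at least one dose, as now required, and complete the 21 days without a DLT.

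Keeping the dose requirement in the second condition prevents a patient with a trivial partial infusion from counting as a full DLT-free observation. Record the change in SAP 12.0, and check that every patient with an in-window DLT in the SAP 7.6.1 listing is in the set. Amending the replacement rule in Protocol 5.2.3.4 would no longer affect this trial.

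The cost is one sentence, one re-derived flag and one line in SAP 12.0, with no new data. The small downside is a slightly conservative (higher) rate, because patients who leave early without a DLT stay excluded: 26.0% against a true 25% in the example above.
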